## 7.2 Secondary Efficacy Endpoints Evaluation

### 7.2.1 Key Secondary Endpoint: Global Severity Score (GSS)

- As key secondary endpoint, a formal comparison for change from baseline in GSS (see Section 14.3.2 for computation details) to Day 2, 5 hours post dose will be performed using a contrast analysis on a longitudinal mixed model with random factor subject and fixed effects baseline value, treatment group and timepoint including the treatment-by-timepoint interaction term. All data up to and including Day 3 will be used in the longitudinal mixed model. The Kenward-Roger approximation of degrees of freedom will be used. The model will initially be fitted using an unstructured variance-covariance matrix. In case of non-convergence this may be replaced with a autoregressive variance covariance matrix with heterogeneous variance (ARH) to achieve convergence of the model. The individual pair-wise comparisons will be reported. No formal multiplicity correction will be performed. This comparison will be performed for mITT, RSV infected and PP population.
- For GSS and each of the GSS subitems where GSS is not missing, descriptive statistics will be provided for the actual values and the change from baseline for all planned timepoints. In addition to these planned timepoints, a separate timepoint (Day of hospital discharge) will be created using the last value on the date of discharge from the hospital for GSS summary tables.
- The mean GSS  $\pm$  SE will presented graphically over time (excluding the in-hospital post-treatment assessments), as well as the mean change from baseline  $\pm$  SE. Two bar charts will be provided. One bar chart will present the mean GSS and contributing subitems at all timepoints up to Day 3, 2 hours post dose. The second bar chart will present the mean GSS and contributing subitems over the whole study period (excluding the in-hospital post-treatment timepoints), but will for the first 3 days only include the pre-dose assessments.

Descriptive statistics and figures will be performed on both mITT and RSV infected population

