**Timing of assessments:** post-dose time points relate to the end of the 2nd of the 2 nebulizations of study drug administration. Pre-dose time points relate to the start of the 1st of the 2 nebulizations of study drug administration. Throughout the study, study personnel should make every reasonable effort to follow the timing in the schedule of assessments for each subject.

- a. If the Day 1 pre-dose assessments will be performed within 3 hours after the screening assessments have been performed, the assessments already done at screening do not need to be repeated and only the additional assessments to be performed on Day 1, pre-dose will need to be performed.
- b. At the time of randomization, subjects should be eligible for study participation as defined in the inclusion/exclusion criteria. Therefore, at a minimum, the SpO2, feeding, respiratory muscle retractions, and respiratory rate should be evaluated on Day 1 before randomization, unless these assessments were already performed within the last 3 hours before randomization.
- c. Study drug administration should take place within 24 hour intervals ( $\pm$  4 hours) relative to the start of the 1st nebulization of the 1st dose. Provided that the clinical response criteria have been met, discharge from the hospital can take place per protocol at the Investigator's discretion from dosing Day 2 onwards after all required assessments of the 5 hours ( $\pm$  1 hour) post-dose time point have been completed. Subjects who started study drug dosing but were discontinued prematurely from study drug treatment, should be further monitored according to the in-hospital post treatment period (if applicable) and should attend the FU and EOS visits.
- d. The in-hospital post-treatment assessments are to be performed for subjects who are not discharged from the hospital after the completion or discontinuation of study drug treatment.

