### **3.4.1.3. FOLLOW-UP AND END-OF-STUDY VISITS**

Subjects who have received at least one dose of study medication should complete a FU visit on Day 14 ± 2 days and an EOS visit on Day 28 ± 2 days.

In case a subject is re-hospitalized or consults the Investigator for a respiratory condition after hospital discharge, an unscheduled visit is to be performed. At a minimum this is to include collection of a mid-turbinate nasal swab, lung auscultation and physical examination.

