## 5.4 General Methods

### 5.4.1 Summary statistics

For continuous variables, descriptive statistics will be presented. Descriptive statistics will include the number of non-missing data points (n), the arithmetic mean, the standard deviation (SD) (for baseline summaries) and standard error (SE) (for post-baseline or change from baseline summaries), the median, minimum and maximum.

Descriptive statistics of the baseline global severity score (GSS) will additionally include quartiles (Q1 and Q3).

Descriptive statistics of the pharmacodynamic parameter Krebs von den Lungen-6 (KL-6) and of the study drug concentrations by ADA and Nab subject classifications will additionally include 5% and 95% percentiles, geometric mean, geometric SD and coefficient of variation (CV)% of arithmetic mean.

For categorical variables, frequency tabulations will be presented, consisting of frequency counts and percentages. Missing observations (counts) will be tabulated as a separate category but not taken into account for calculating percentages (denominator for percentages is total of non-missing observations within the group). Both zero count categories (rows) within a parameter as well as treatment groups without counts/events (columns) will be shown in the tables .

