## 7.3 Other Efficacy Analyses

- Evolution over time in clinical symptoms will be evaluated. The body temperature and respiratory rate (actual values, change from baseline and percent change from baseline) will be summarized descriptively over time. Frequency tabulations will be provided to summarize the feeding, respiratory distress parameters (Wheezing (during inspiration/expiration), lung fields affected, crackles/crepitations, respiratory muscle retractorations (supravascular, intercostal and subcostal) , cough and general appearance of the subject over time. Respiratory rate and body temperature will also be presented graphically in mean  $\pm$  SE plots (excluding the in-hospital post-treatment timepoints).
- Respiratory Distress Assessment Instrument (RDAI) and Respiratory Change Score (RACS) will be calculated (see Section 14.2.3 and 14.2.4 for calculation method, respectively) . Actual values (RDAI, RACS) and changes from baseline (RDAI) will be summarized over time using descriptive statistics (both subitem and totals). RDAI, change from baseline in RDAI and RACS will also be presented graphically in mean  $\pm$  SE plots (excluding the in-hospital post-treatment timepoints). Similar to GSS, bar charts will be generated for RDAI to visualize contributing subitems.
- Length of hospital stay (in days – see section 14.2.9 for calculation method) defined as time between admission and discharge for the initial hospitalization will be summarized as descriptive statistics and using KM estimates. In case of missing discharge information the subject will be censored on date(time) of trial termination.
- The time between first study drug administration and discharge (in days) for the initial hospitalization will be summarized as descriptive statistics and using KM estimates. In case of missing discharge information the subject will be censored on date(time) of trial termination.

- Length of hospital stay for RSV: The time between hospital admission and discharge (in days) excluding prolongation due to SAE other than RSV worsening. Time will be summarized as descriptive statistics and using KM estimates. In case of missing discharge information the subject will be censored on date(time) of trial termination. If needed time will be imputed with 18u00 (see section 14.2.10 for calculation details).

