#### 14.2.2 Global Severity Score (GSS)

GSS will be calculated by summing the scores of 7 individual items (see below). Maximum score is 20 with higher score indicating a more severe disease.

For the computation of the baseline GSS, the baseline value of each individual item is first identified (some may be from Day 1 pre-dose and others from screening). The individual item baseline values are then summed to obtain the baseline GSS.

Apnea, hospital stay, oxygen supplementation, and ventilation will be considered respectively to have occurred at the considered visit and time point if they are reported over a period that covers at least partly the time interval defined for this visit using following definitions for time intervals:

- for baseline : from hospital admission to first study drug administration,
- for post-baseline visits and timepoints during treatment as:
  - starting from the minimum between:
    - the end of the previous interval,
    - the earliest date and time a GSS component was assessed at the considered visit and timepoint, and
    - 1 minute before the latest date and time a GSS component was assessed at the considered visit and timepoint

- - ending at the latest date and time a GSS component was assessed at the considered visit and timepoint.
- for all ‘Post-Treatment Day n’ visits:
  - the “MORNING” timepoint will be assigned to time interval 00:00 – 11:59 of the date of the considered visit and timepoint
  - the “EVENING” timepoint will be assigned to time interval 12:00 – 23:59 of the date of the considered visit and t timepoint
- The “Follow-UP” visit and unscheduled post-treatment visits will be assigned to time interval 00:00 – 23:59 of the date of the considered visit and timepoint. This implies that there will be a gap between the follow-Up visit and the previous timepoint, and that every hospitalization / apnea / ventilation / oxygen supplementation recorded that would be entirely within that gap will not be taken into account into GSS score computed at any timepoint.

This implies that a recorded item (hospitalization / apnea / ventilation / oxygen supplementation) may contribute to more than one time interval for the GSS calculation.

Item	Number of Points	Description
Feeding	0	Adequate oral feeding
	1	No adequate oral feeding, occasional breaks during feeding
	2	No adequate oral feeding, frequent breaks during feeding
	3	No adequate oral feeding, unable to feed, or on feeding support

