- q. 48 subjects will undergo more extensive PK analysis (3 PK samples per subject instead of the 1 sample), i.e., blood draws on Days 2-3 1) pre second dose, 2) at any time between 0.5 hours and 3 hours post second dose, and 3) at any time between 3 hours and 6 hours post second dose (and at least 1 hour apart from the previous sampling); If sufficient serum remains after PK assessment, exploratory biomarker (KL-6) may also be evaluated.
- r. Blood draw at screening for clinical laboratory (hematology and clinical biochemistry) and immunogenicity. If sufficient serum remains after immunogenicity assessment, exploratory biomarker (KL-6) may also be evaluated. In case the blood sample for immunogenicity was not taken at screening, the sample should be collected at the Day 1 pre-dose timepoint, as far as possible.
- s. Blood draw on Day 14 for clinical laboratory (hematology and clinical biochemistry) and immunogenicity. If sufficient serum remains after immunogenicity assessment, exploratory biomarker (KL-6) may also be evaluated. No blood sample needs to be taken in case of premature withdrawal from the study for subjects who did not receive any study drug. In case the blood sample for immunogenicity was not taken on Day 14, the sample should be collected at the EOS (Day 28) visit, as far as possible.
- t. In case of a severe and/or serious hypersensitivity reaction, an additional serum sample should be collected (if reasonably feasible) as soon as possible after the start of the event.
- u. For Day 3, the 5 hour post dose assessments are only applicable for sites in Germany.

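### Between Day 3 and Day 14 the by-arm GSS, RDAI and symptom tables describe only infants still in hospital, so those rows are not like-for-like comparisons of the arms

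*SAP*

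**What the plan says.** - **Who is assessed.** Protocol, Schedule of Assessments, footnote d: "The in-hospital post-treatment assessments are to be performed for subjects who are not discharged from the hospital". Infants discharged after dose 2 must return for dose 3, so every infant is scheduled up to Day 3, 2 h post dose. The next clinic visit for everyone is Day 14: "Subjects who have received at least one dose of study medication should complete a FU visit on Day 14" (Protocol 3.4.1.3).
- **What is tabulated.** SAP 7.2.1, on GSS and its subitems: "descriptive statistics will be provided for the actual values and the change from baseline for all planned timepoints". SAP 14.2.2 defines a morning and an evening GSS interval for each post-treatment day, so these are planned timepoints. SAP 7.3, on symptoms over time: "Frequency tabulations will be provided to summarize the feeding, respiratory distress parameters", followed by cough and general appearance. SAP 7.4 repeats the GSS table by subgroup.
- **Denominators.** SAP 5.4.1: "denominator for percentages is total of non-missing observations within the group". The same section requires n for continuous summaries and a count of missing observations for categorical ones.
- **Discharge timepoint.** SAP 7.2.1 adds for the GSS tables: "a separate timepoint (Day of hospital discharge) will be created using the last value on the date of discharge".
- **Figures.** SAP 7.2.1 and 7.3 leave the in-hospital post-treatment timepoints out of the mean plots for GSS, RDAI, RACS, respiratory rate and temperature, and out of the GSS bar chart that runs past Day 3. The tables carry no such exclusion.

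**The concern.** Discharge happens after randomisation and can be affected by treatment. Under the Protocol it requires adequate oral feeding and stable saturation on room air, and feeding is itself a GSS item. A post-treatment row therefore compares the infants in each arm who have not yet recovered enough to leave. If one arm recovers faster, its row holds a smaller and more strongly selected remainder.

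The GSS itself sharpens the problem. Its medical-interventions item scores 0 only for an infant who is out of hospital and at least 1 for any inpatient. The scale gives credit for discharge, but no infant in an in-hospital row can receive it.

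The day-of-discharge GSS has a related fault: it compares arms at different elapsed times, at a moment largely defined by recovery.

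What is at stake is how the descriptive tables are read. Table 14.2.1.7 is flagged as topline, and Protocol 3.1.2 says the study will support the choice of dose and of endpoints for later development.

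**Working it through.** **1. The plan's own GSS figure.** The only stated figure is 80% power for a 2-point difference at Day 2 (SAP 4.2: SD 3.2, two-sided 0.05, 45 per arm, 15% drop-out). With n = 45 x 0.85 = 38.25 per arm, power = Phi(2 / (3.2 x sqrt(2/38.25)) - 1.96) = Phi(2.73 - 1.96) = 78.0%; with n = 45 it is 84.2%. The stated 80% is roughly reproduced. It concerns Day 2, when on-protocol infants are all inpatients, so it says nothing about the later rows.

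**2. Are discharged infants filled in?** No. SAP 14.2.2 sets GSS to missing when more than two of six named items are missing. For a discharged infant five of the six are unassessed (feeding, RDAI, respiratory rate, general appearance, temperature). SAP 14.2.3 imputes nothing for RDAI.

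**3. Percentages (hypothetical arithmetic).** Suppose 40% of placebo and 20% of active infants are still in hospital on some day, and 75% of those in each arm feed inadequately. On non-missing denominators the table reads 75% v 75%. On the full denominator it reads 0.40 x 0.75 = 30% v 0.20 x 0.75 = 15%, with 60% v 80% discharged.

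**4. Means (illustration; no input below comes from the documents).** Baseline GSS mean 10, SD 2.5; placebo decline 1.5 points per day, SD 0.7; drug adds 0.5 or 0.9 points per day; score floored at 0; discharge from Day 2.2 once the score plus noise (SD 1) is 4 or less, or 6 or less; 200,000 infants per arm. Differences are active minus placebo. The all-infant column keeps discharged infants at their modelled score. Day 5:

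| Discharge at | Drug adds per day | In hospital, placebo v active | All infants | In hospital, actual value | In hospital, change |
|---|---|---|---|---|---|
| 4 | 0.5 | 49% v 29% | -1.50 | -1.00 | -1.58 |
| 4 | 0.9 | 49% v 17% | -2.31 | -1.68 | -2.75 |
| 6 | 0.5 | 28% v 14% | -1.50 | -0.82 | -1.48 |
| 6 | 0.9 | 28% v 7% | -2.32 | -1.40 | -2.57 |

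Over Days 4 to 7:
- Actual values: the in-hospital difference is smaller by between 1 - 1.42/1.62 = 12% (Day 7, threshold 4, 0.9 per day) and 1 - 0.73/1.35 = 46% (Day 6, threshold 6, 0.5 per day).
- Change from baseline: the ratio to the all-infant difference runs from 1.45/1.54 = 0.94 (Day 4, threshold 6, 0.5 per day) to 2.50/1.62 = 1.54 (Day 7, threshold 4, 0.9 per day). One reason it can exceed 1 is that recovered infants in both arms reach the floor, which shrinks the all-infant difference.

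**5. A second set of assumptions.** A 2-point benefit, decline 1.3 per day (SD 0.6), within-infant SD 1.5 and discharge at an observed GSS of 5 or less give, at Day 5, about 45% v 23% in hospital. The all-infant difference is about -1.7. The in-hospital difference is about -0.6 for actual values (1 - 0.6/1.7 = 65% smaller) and about -1.5 for change (1.5/1.7 = 0.88). Handling the floor differently moves these by 0.1 to 0.2 points and leaves the actual-value difference near one third of the all-infant one.

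**The case against.** A reader might infer that a drug which speeds discharge would have its clinical effect masked. The documents do not support that:

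- The only formal GSS comparison is at Day 2, 5 h post dose, from a model using data to Day 3. Inpatient stay is required on Days 1 and 2, and discharged infants return on Day 3.
- Faster recovery and discharge have their own Kaplan-Meier analyses: time to clinical response (also topline), first dose to discharge, length of stay and duration of severe disease.
- The affected rows carry no test, and the main figures already omit these timepoints.

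Nor is it right that only inpatients are assessed after Day 3. Day 14 covers every dosed infant and has its own GSS interval; SAP 14.2.2 itself notes "This implies that there will be a gap between the follow-Up visit and the previous timepoint". The caregiver diary scores cough, wheeze and trouble breathing daily to Day 28, in or out of hospital.

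It is also fair that n and missing counts will show the groups shrinking, and that the simulations rest on invented inputs. Per-protocol discharge turns on feeding, saturation and Investigator discretion, not on a GSS cut-off, and the plan's 2-point effect belongs to Day 2.

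Finally, one might add the V1.0 timepoint described as "For Day 3, the 5 hour post dose assessments are only applicable for sites in Germany". That subset is defined by country, not by a post-randomisation outcome, so it does not share this fault.

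What remains is narrower. A missing count does not separate a discharged infant from a missed assessment, and the other analyses do not make these rows comparable. For feeding, respiratory-distress signs, cough and general appearance, the clinic-assessed summaries over time are these frequency tables, with no mean plot of their own.

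**Conclusion.** The point holds for the descriptive by-arm rows between Day 3 (2 h post dose) and Day 14 in SAP 7.2.1, 7.3 and 7.4, and for the day-of-discharge GSS. They condition on still being in hospital, and the SAP attaches no caveat. That much follows from the documents without any simulation.

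The size does not. On the assumptions shown, differences in actual values are attenuated, by 12% to 46% in one set and about 65% in the other. Differences in change from baseline can go either way (0.88 to 1.54 times the all-infant value). The real distortion could lie outside these ranges.

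No formal conclusion of the trial is at risk. This is an inexpensive improvement to how the tables can be read, not a flaw in the key secondary analysis.

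**What to change.** For the in-hospital post-treatment timepoints:

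1. **Symptom frequency tables (Tables 14.2.4.5 to 14.2.4.8: feeding, respiratory distress, cough, general appearance).** Use the full mITT denominator per arm, with discharged as a category separate from missing. The rows then describe all randomised and dosed infants, using data already collected.
2. **GSS and RDAI means, including the subgroup GSS table (14.2.8.2).** Either drop these timepoints, as the figures already do, or show the number still in hospital per arm and label the rows *conditional on still being hospitalised; not for between-arm comparison*. The RACS, respiratory-rate and temperature means in SAP 7.3 can follow the same rule.
3. **Day-of-discharge GSS.** Keep it if wanted, with the same label.
4. **Heart-rate safety table (SAP 8.4).** Leave it in place with the same label, so that safety data on the infants who stay longest are not lost.

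The cost is SAP wording and slightly longer table shells, with no new data. There would be no directly comparable mean GSS by arm between Day 3 and Day 14, but the present rows do not provide one either.

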## 7.2.2 Other Secondary Endpoints

### 7.2.2.1 Clinical Response

Clinical response is defined as achieving adequate oxygen saturation and adequate oral feeding. The time to clinical response (hours), defined as the time between the first study drug administration and achieving clinical response, will be summarized using KM estimates and presented graphically. Subjects who already achieved clinical response before the start of dosing, will be excluded from the analysis.

The time to achieving adequate oxygen saturation and the time to achieving adequate oral feeding will be summarized similarly. Subjects who already achieved adequate oxygen saturation or already achieved adequate oral feeding before the start of dosing, will be excluded from the analysis, respectively.

The time to event for subjects with missing data and/or who did not reach the clinical response for oxygen saturation and oral feeding during the trial will be censored at the last nonmissing assessment of blood oxygen level in the vital signs domain (VSTESTCD=OXYSAT) or assessment of adequate oral feeding (DCTESTCD=FEDADQ) If only one condition is reached, then the time to clinical response is censored at the last non missing assessment of the condition which was not met. The same rule will be applied for the time to achieving adequate oxygen saturation and the time to achieving adequate oral feeding.

### 7.2.2.2 Viral Load

In this study, viral titers are measured using the plaque assay for the primary endpoint and by RT-qPCR for the secondary endpoint(s). As secondary endpoint, the time to BQL using RT-qPCR will be summarized using KM estimates. No p-values will be provided.

The time to undetectability (hours) defined as the time from the first study drug administration to first occurrence of viral titer below the lower limit of quantification (LLOQ) and target not detected, provided the next measured value is below the quantification limit and undetected as well, will be summarized using KM estimates, based on the plaque assay and RT-qPCR. The time to event for subjects with missing data and/or who did not reach undetectability during the trial will be censored at the last nonmissing viral load assessment .

In addition, the number and percentage of subjects that have viral titers BQL (for both virus and RNA) and with undetectable viral load will be tabulated over time.

Viral load measured by plaque forming unit assay (log10 PFU/mL) and by RT-qPCR (log10 viral copies/mL) will be summarized as continuous variables:

- Viral load (actual values and absolute change from baseline) in nasal swab specimens (RT-qPCR and plaque assay) will be presented using descriptive statistics (see section 5.4.1) over time. Viral load will also be presented graphically by plots describing the mean over time (+SE).

For the summary statistics, samples that are below the lower limit of quantification (LLOQ) (i.e. BQL) will be assigned a value of half the LLOQ level.

- Time weighted average change from baseline up to Day 3 and Day 14 (both virus and RNA) (see section 14.3.1 for calculation method).

Viral load analysis will be performed on mITT and RSV infected population

